### 4.2 Secondary Outcome Measures

1. Proportion of subjects with Target Lesion Primary Patency at months 12 and 24.
  2. Proportion of subjects with Assisted Target Lesion Primary Patency (aTLPP) at months 6, 12 and 24 defined as time to loss of Assisted Primary Patency of the target lesion, which is the time from post-procedure until uncorrectable target lesion occlusion.
  3. Proportion of subjects with Access Circuit Primary Patency (ACPP) at months 6, 12 and 24 defined as time to loss of Primary Patency of the access circuit, which is the time from post-procedure until any venous outflow circuit re-intervention, or access thrombosis or abandonment.
  4. Proportion of subjects with Post-Procedure Secondary Patency at months 6, 12 and 24 defined as the interval post-procedure until access circuit abandonment.
  5. Rates of procedure- and device-related adverse events involving the access circuit at index procedure, 30 days, and months 6, 12 and 24.
- 

[figure not shown]
[figure not shown]

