#### 5.4 Subject Withdrawal

Subjects may withdraw at any time from the clinical trial without jeopardy or prejudice. If a subject prematurely terminates from the study, the reason for study termination will be recorded and the results will be tabulated by number and percent for each category. If termination is a result of an adverse event or death, an Adverse Event Form will also be completed. Subjects who withdraw consent after treatment will have their data evaluated until the time of their withdrawal.

The Investigator should follow all unresolved SAEs until the events are resolved, the subject is lost to follow-up, the subject has withdrawn consent, the subject completes the study, or the adverse event is otherwise explained.

All reasonable efforts will be made to obtain complete data for all subjects; however, missing observations will occur due to lost to follow-up, withdrawal, or non-adherence with required assessments. Three (3) attempts shall be made to contact subjects who do not return for study follow-up visits. The final attempt shall include a certified letter to the subject regarding study participation. If these subjects cannot be located, they will be considered lost to follow-up. If they are contacted but refuse to return for visits, they

will be considered withdrawals. If they actively request to withdraw from the study, they will be considered withdrawals. Subjects shall be encouraged to complete a final study exit visit at the time of withdrawal to assess for safety. Data collected up to the time of loss to follow-up or withdrawal will be maintained in the study database and used for analysis purposes, as appropriate. These subjects will not be replaced.

Subjects should be withdrawn from the study by the Investigator if any of the following occur as these additional treatments prevent further analysis of patency related endpoints:

- Subject proceeds to renal transplant
- Device is explanted
- Access is abandoned

Investigator may also withdraw subjects from the study for reasons other than above, where they judge this is in the subject's best interest. Data collected up to the time subject is withdrawn from the study will be maintained in the study database and used for analysis purposes, as appropriate. These subjects will not be replaced.

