## 9.8 Handling of Missing Data

For all primary, secondary and exploratory analyses, no imputation of missing data is planned. In general, endpoint rates will be calculated as the number of subjects who had an endpoint prior to the milestone visit divided by the number of evaluable subjects who had sufficient follow up (e.g., at least 150 days for 6-month visit) plus any subjects who had an event prior to the milestone visit. In other words, the denominator will be adjusted for missing follow up data. A tipping point analysis will be done on the primary endpoints as a missing data sensitivity analysis. This analysis encompasses all possible imputation outcomes and thus is a rigorous set of sensitivity analyses.

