## 9.10 Analysis

For the randomized AVF Peripheral cohort, the count and percentage of subjects with TLPP at 6 months will be presented by treatment arm. The percentages will be computed as

$\hat{p}_i = 1 - \frac{n_i}{m_i}, i = T(\text{treatment}), C(\text{control})$ .  $n_i$  is the number of subjects in each treatment arm who experienced non-patency event within 180 days post procedure,  $m_i$  is the number of subjects in each

treatment arm who experienced non-patency event within 180 days or had no non-patency event but followed up for at least 150 days. The hypothesis will be tested using the chi-square test, and the differences between treatments together with a two-sided 95% confidence interval will be calculated. For the primary safety endpoint, the count and percentage of subjects with a safety event at 30 days will be presented by treatment arm. The percentages will be computed as  $\hat{p}_i = 1 - \frac{n_i}{m_i}$ ,  $i = T, C$ .  $n_i$  is the number of subjects in each treatment arm who experienced an event within 30 days post procedure,  $m_i$  is the number of subjects in each treatment arm who experienced an event within 30 days or had no event but followed up for at least 23 days. Non-inferiority on the safety endpoint will be tested using the Farrington-Manning test. The differences between treatments together with the one-sided 95% upper confidence limit will be calculated.

For the nonrandomized AVG Anastomosis cohort, a one-sided p-value will be derived based on an exact binomial test. The study device will be considered to have achieved the primary effectiveness objective if the one-sided p-value is less than 0.05. Or equivalently, the lower limit of the one-sided 95% confidence limit based on exact method is greater than 60%. The same testing methodology will be used for the primary safety endpoint in comparison to the PG of 89%.

To control the overall Type I error (two-sided  $P=0.05$  superiority and one-sided  $P=0.05$  non-inferiority) in the randomized cohorts the following fixed sequence testing procedure will be taken:

Primary effectiveness superiority; if significant at two-sided  $\alpha=0.05$ , proceed to

Primary safety non-inferiority; if significant at one-sided  $\alpha=0.05$  proceed to secondary endpoints.

The key secondary effectiveness endpoint with hypothesis testing is TLPP at 12 months (360 days). Other secondary effectiveness endpoints for hierarchical testing, in order, are:

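### Device explant or access abandonment that is not recorded as a patency event can drop a subject from the 6-month TLPP denominator, or leave the subject counted as patent

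*Combined protocol and SAP*

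**What the plan says.** Section 5.4 (Subject Withdrawal) states: "Subjects should be withdrawn from the study by the Investigator if any of the following occur as these additional treatments prevent further analysis" of the patency endpoints. It gives three triggers: renal transplant, "Device is explanted" and "Access is abandoned". On the data already in hand it says: "Data collected up to the time subject is withdrawn from the study will be maintained in the study database and used for analysis purposes", qualified by the words as appropriate.

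Section 9.10 puts two kinds of subject in the TLPP denominator: those with a non-patency event within 180 days, and those who "had no non-patency event but followed up for at least 150 days". Section 9.8 plans no imputation and says that "the denominator will be adjusted for missing follow up data". It adds a tipping point analysis of the primary endpoints as a sensitivity analysis. Section 9.2 censors a subject in the Kaplan-Meier analysis when the subject becomes un-evaluable.

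No section names explant or abandonment as a TLPP event, and the wording of the TLPP event differs between sections:
- **Section 4.1.2:** clinically driven target lesion revascularization, target lesion thrombosis, or uncorrectable target lesion occlusion.
- **Section 9.3.2:** the next intervention on the target lesion only.
- **Section 13.0:** access circuit thrombosis in place of target lesion thrombosis. It also defines a clinically driven revascularization as one accompanied by signs of access dysfunction.
- **Section 9.10:** a non-patency event, not defined further.

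Section 4.2, by contrast, makes abandonment a component of ACPP and the end of secondary patency, which is "the interval post-procedure until access circuit abandonment".

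**The concern.** Transplant can reasonably be treated as ending patency observation for reasons unrelated to the lesion. Explant and abandonment are different, because they usually mean that the device or the access has failed. Section 5.4 nevertheless handles all three alike. It describes abandonment as something that prevents patency analysis, although the plan itself uses abandonment as a patency outcome elsewhere.

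If such failures leave the primary denominator, the patency estimate rises in whichever group loses them. Explant can affect only stent graft subjects. PTA leaves no implant, PTA subjects who need a bailout implant at the index procedure are followed only to discharge and replaced (Section 5.3), and a later stent in a PTA target lesion would already be a target lesion intervention. In the single-arm AVG cohort there is no comparator to share the effect, so each dropped failure moves the result toward meeting the 60% goal.

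Withdrawal also ends the planned collection of new safety events and vital status in subjects whose device has been removed.

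**Working it through.** **1. The plan's own figures.**
- AVF inputs (Section 9.7): 78% vs 60%, two-sided 0.05, 80% power, 85% compliance. n per arm = [1.960·√(2·0.69·0.31) + 0.842·√(0.78·0.22 + 0.60·0.40)]² / 0.18² = (1.282 + 0.540)² / 0.0324 ≈ 102.5, so 103. Then 103/0.85 = 121.2, so 122. Both agree with the plan.
- AVG inputs (Section 9.7): 74% vs a goal of 60%, one-sided 0.05, exact binomial, n = 96. The smallest passing count is 66, since P(X ≥ 66 | 96, 0.60) = 0.0484. Power is P(X ≥ 66 | 96, 0.74) = 0.8995. Then 96/0.85 = 112.9, so 113. Both sizes agree with the plan.

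**2. How a subject is routed.** Sections 5.4, 9.8 and 9.10 together give:

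| Explant or abandonment | TLPP event recorded by day 180 | No TLPP event recorded |
|---|---|---|
| Before day 150 | In denominator, failure | Out of denominator |
| Days 150–179 | In denominator, failure | In denominator, patent |

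The right-hand column is the problem. It can hold an explant for infection without access dysfunction. Under the Section 9.3.2 wording it can also hold an uncorrectable occlusion that leads to abandonment with no intervention.

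**3. AVG type I error.** The documents give no explant or abandonment rate, so the size is an assumption. Let f be the share of all AVG subjects who are failures dropped in this way. At a true 60%, patency among those remaining is 0.60/(1−f). Type I error is P(X ≥ 66 | 96, 0.60/(1−f)).

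| f | Patency among those counted | Type I error |
|---|---|---|
| 0 | 60.0% | 4.8% |
| 1% | 60.6% | 6.2% |
| 3% | 61.9% | 9.8% |
| 5% | 63.2% | 15.1% |

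The base matters. If 3–5% of failures (not of all subjects) were dropped, then f = 0.40 × 3–5% = 1.2–2.0% and the error is 6.5–7.8%.

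**4. Results at the planned rates.** Dropped subjects are returned to the denominator as failures.
- AVG: 0.74 × 96 ≈ 71. 71/96 = 74.0%. With five returned, 71/101 = 70.3%, exact one-sided p = 0.021, and the goal is still met.
- AVF: 0.78 × 103 ≈ 80 and 0.60 × 103 ≈ 62. Pearson χ² = N(ad−bc)² / (product of the margins), with PTA at 62/103. For 80/103, χ² = 206·1854²/(103·103·142·64) = 7.34, p = 0.007. With three returned (80/106 = 75.5%), χ² = 209·1668²/(106·103·142·67) = 5.60, p = 0.018. With five returned (80/108 = 74.1%), χ² = 211·1544²/(108·103·142·69) = 4.62, p = 0.032. Superiority stands in each case.

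**5. Borderline results.**
- AVG: 66/96 gives p = 0.048 and passes; 66/97 gives p = 0.064 and fails.
- AVF against 62/103: 76/103 gives p = 0.038; with two returned, 76/105 gives p = 0.063.

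**6. Power and false wins in AVF.** With 78% of 103 counted as patent and k stent graft failures returned, power falls from 80.2% to 76.7% (k=1), 68.9% (k=3) and 60.7% (k=5). If true patency is 60% in both arms and k failures are dropped from the stent graft arm alone, the chance of a false stent graft win rises from 2.5% to 3.7% (k=2), 4.5% (k=3) and 6.5% (k=5).

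**The case against.** The case on the other side has real substance.

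- **Many such subjects are already failures.** Abandonment often follows thrombosis, a target lesion intervention or an uncorrectable occlusion, and a subject with any of these recorded stays in the denominator. Removing a device from the target lesion is arguably itself an intervention on it under Section 9.3.2, and the CEC reviews all site-reported conduit interventions (Section 12.10). This limits the number affected. It does not settle the matter, because Section 4.1.2 requires the revascularization to be clinically driven and the sections disagree.
- **The effect would be visible.** The tipping point analysis covers the case in which every dropped stent graft subject is a failure, and Section 5.4 tabulates reasons for termination. That is correct, but the primary estimate and the success decision do not change. The Kaplan-Meier analysis censors the same subjects as if withdrawal carried no information.
- **Safety follow-up does not stop altogether.** A reader might infer that withdrawal ends it. Sections 5.4 and 7.0 list withdrawal of consent, not withdrawal by the investigator, among the points at which follow-up of an unresolved SAE may stop, and Section 5.4 encourages an exit visit. What is lost is new later events and vital status.
- **The bias is not one-sided throughout.** A reader might infer that it is. That holds for explant only. Abandonment can occur in both AVF arms, and dropped PTA abandonments would favour PTA.

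**Conclusion.** The gap is real and lies in the rules themselves: a stated withdrawal trigger combined with a stated denominator can remove failures from the primary TLPP analysis before day 150, or score them as patent on days 150–179. Explant acts on stent graft subjects only. Abandonment biases the AVF comparison only if its rate differs between arms. In the AVG cohort every dropped failure favours the device.

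The size cannot be fixed from the documents and may be small. Type I error of about 6–15% in the AVG cohort rests on the assumption that 1–5% of all its subjects are dropped failures. A reader might infer that the plan's error rate is therefore 10–15%, or that the trial's conclusions would not survive. The documents support neither: they give no rate, and at the planned rates three to five such subjects reverse neither cohort's result. Only a borderline result would be at risk. The change should be made because it is cheap and removes a choice that would otherwise be made after the data are seen.

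**What to change.** - **Section 5.4:** stop using explant and abandonment as reasons for study withdrawal. Keep these subjects in follow-up for new safety events and vital status. This concerns data collection only and does not touch the clinical decision to explant or abandon.
- **Sections 9.3.2 and 9.10:** in the primary analysis, count explant of the study device before day 180 as a TLPP non-patency event on its date. Count abandonment in the same way unless the CEC adjudicates the target lesion patent and the cause unrelated to it. Report the version that drops these subjects as a sensitivity analysis.
- **TLPP wording:** reconcile Sections 4.1.2, 9.3.2, 9.10 and 13.0 so that one list of events applies throughout.
- **Leave unchanged:** the ACPP and secondary patency definitions. Abandonment already ends both, and counting explant as loss of secondary patency would redefine an endpoint that ends at abandonment.

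The cost is a protocol amendment with matching analysis wording, and continued follow-up of a few subjects. Stent graft patency may come out slightly lower.

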Subject Population:	
The study comprises 2 independent cohorts:
 
 
Subjects with AVF for hemodialysis who have stenosis or occlusion of the peripheral venous outflow circuit, including the cephalic arch,
 
Subjects with AVG for hemodialysis who have stenosis or occlusion at the graft-vein anastomosis or juxta-anastomosis
 
								
Clinical Sites:	Up to a total of 50 centers with up to 15 international centers.								
Study Follow-Up:	After the index procedure on Day 0, subjects shall be evaluated within the clinic at 30 days, then at months 6, 12 and 24. Telephone follow-up shall be completed at months 3, 9 and 18.								
Anticipated Study Duration:	
 
 First subject enrolled (actual):	March 2021	
 
 Last subject enrolled (all cohorts):	December 2023	
 
 Last subject completes Month 6 Visit:	June 2024	
 
 Last subject completes Month 24 Visit:	January 2026	
 
	First subject enrolled (actual):	March 2021	Last subject enrolled (all cohorts):	December 2023	Last subject completes Month 6 Visit:	June 2024	Last subject completes Month 24 Visit:	January 2026
First subject enrolled (actual):	March 2021								
Last subject enrolled (all cohorts):	December 2023								
Last subject completes Month 6 Visit:	June 2024								
Last subject completes Month 24 Visit:	January 2026								
Primary Outcome Measures:	
Primary Safety Endpoint: Proportion of subjects without any localized or systemic safety events through 30 days post-index procedure that affect the access or venous outflow circuit and resulted in reintervention, hospitalization, or death (not including stenosis or thrombosis). Endovascular procedures performed to treat safety events after the index study procedure will be considered surgeries.
 
Primary Effectiveness Endpoint: Proportion of subjects with Target Lesion Primary Patency (TLPP) at 6 Months. TLPP is defined as freedom from clinically-driven target lesion revascularization (CD-TLR) or target lesion thrombosis measured through 6 months post-procedure, which is the time interval of uninterrupted patency after study procedure to the next intervention performed on the target lesion or uncorrectable target lesion occlusion.
								

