### **6.4.3. Randomization**

Randomization will be used to reduce potential bias during data collection and evaluation of clinical endpoints in the AVF Peripheral cohort. Randomization schedules will be generated using block randomization that will control the balance of treatment groups within each site and across the study. It is not possible for treating physicians to be blinded to the treatment group. Subjects who receive a Merit WRAPSODY Stent Graft must receive a device information card to provide to health care givers in the event they undergo an MRI, so subjects cannot be blinded.

AVF Peripheral subjects will be randomized 1:1 to receive either the Merit WRAPSODY Stent Graft (SG) or PTA. AVG Anastomosis subjects will not be randomized. Once baseline angiography confirms eligibility, including confirmation of reference vessel diameter (RVD), lesion length, full expansion of the predilatation balloon, the patient is eligible to be randomized or enrolled in the AVF Anastomosis cohort.

Subjects randomized to the PTA arm (control) will undergo standard percutaneous balloon angioplasty. Subjects randomized to receive treatment with the Merit WRAPSODY Stent Graft after predilatation will undergo stent graft placement as outlined in Section 6.4.4. Only the target lesion will be treated with the WRAPSODY stent graft.

Note: Subjects in the AVG Anastomosis cohort will all receive treatment with the Merit WRAPSODY Stent Graft as this cohort is non-randomized.

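### Section 5.4 lets an unblinded investigator end a subject's patency follow-up at discretion; if likely failures leave this way, false success can exceed its nominal rate, mainly in the single-arm AVG cohort

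*Combined protocol and SAP*

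**What the plan says.** Section 5.4 names three events after which the investigator should withdraw a subject: renal transplant, explant of the device, and abandonment of the access. It then adds a general ground: "Investigator may also withdraw subjects from the study for reasons other than above, where they judge this is in the subject's best interest". Data up to the withdrawal are kept and the subject is not replaced. The section does not ask for patency outcomes after that date.

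The trial is open label. Section 6.4.3 says of the physicians "It is not possible for treating physicians to be blinded to the treatment group" and of the participants "so subjects cannot be blinded". Treatment is given once, and the rest is follow-up: "After the index procedure on Day 0, subjects shall be evaluated within the clinic at 30 days, then at months 6, 12 and 24" (Protocol Summary). Section 6.3 already leaves post-procedure antiplatelet and anticoagulant use to the investigator, and Section 6.13 already ties reintervention to clinical symptoms.

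For the AVF cohort, Section 9.10 builds the TLPP denominator from subjects with a non-patency event within 180 days and those who "had no non-patency event but followed up for at least 150 days". Section 9.8 gives the general rule that also covers the AVG cohort: nothing is imputed, "the denominator will be adjusted for missing follow up data", and a tipping-point analysis of the primary endpoints serves as a sensitivity analysis.

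**The concern.** With a one-time procedure, leaving the study takes away no study treatment. What ends is the visits and the recording of whether the target lesion stayed open. The person who decides knows what was implanted and can see the access deteriorating, so the decision may be related to prognosis and, in the AVF cohort, to arm.

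The evaluable-only denominator turns that into bias in one of two ways:

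- Withdrawn event-free before Day 150: the subject disappears from both numerator and denominator, and a later failure is never counted.
- Withdrawn event-free between Day 150 and Day 180: the subject counts as patent, even if the lesion fails before Day 180.

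The supportive analyses do not correct this. The Kaplan-Meier estimate censors these subjects (Section 9.2), and the ITT analysis applies the same denominator rule. The tipping-point analysis can expose the problem, but success is decided by the chi-square and exact binomial tests. At stake is the false-success rate for primary effectiveness, most plainly in the AVG cohort, which has no control arm to offset selective loss.

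**Working it through.** **Inputs (Sections 9.7 and 9.10).** AVG: 113 subjects, goal 60%, assumed rate 74%, exact binomial test at one-sided 0.05, 85% compliance. AVF: 122 per arm, 60% for PTA, chi-square test at two-sided 0.05, 85% compliance. Assumed because the documents give no figure: how many subjects are withdrawn, and what share of them would have failed.

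**The plan's own figures.** AVG: with 96 evaluable, the critical count is 66, exact alpha is 0.0484 and power is 0.8995, which rounds to the stated 90%; 96/0.85 = 112.9, so 113. AVF: 78% vs 60% at 80% power gives 103 per arm; 103/0.85 = 121.2, so 122. Both reproduce.

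**Mechanism in the AVG cohort with no other loss.** Let c(m) be the smallest count r with P(Bin(m, 0.6) ≥ r) ≤ 0.05. At m = 113, c = 77 and the false-success rate is 0.046. If two would-be failures leave before Day 150, the number of successes is unchanged but m = 111 and c = 76, so the rate becomes P(Bin(113, 0.6) ≥ 76) = 0.068. With three it is 0.098, and with five 0.137. If failures are instead withdrawn between Day 150 and Day 180 and counted as patent, one, two and three such subjects give 0.068, 0.098 and 0.137.

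**AVG with 15% independent loss.** The evaluable number is n ~ Bin(113, 0.85), successes are Bin(n, 0.6), k subjects are then withdrawn before Day 150, and the critical count is recalculated at n − k.

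| Withdrawn (k) | All certain failures | 60% would have failed |
|---|---|---|
| 0 | 4.0% | 4.0% |
| 2 | about 7% | about 5% |
| 4 | about 11% | 6.4% |
| 6 | about 17% | 8.0% |

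If withdrawal is unrelated to prognosis, the rate stays below 5%. The plan already budgets for 113 × 0.15 ≈ 17 non-evaluable AVG subjects, so two to six discretionary exits would not stand out.

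**AVF with 15% independent loss, true TLPP 60% in both arms.** The chance of declaring stent-graft superiority, when a share of would-be failures is withdrawn, is:

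| Withdrawn, SG | Withdrawn, PTA | False superiority of SG |
|---|---|---|
| 0% | 0% | 2.5% |
| 10% | 0% | 5.6% |
| 10% | 10% | 2.5% |
| 0% | 10% | 1.0% |

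Ten per cent in one arm is about 122 × 0.85 × 0.40 × 0.10 ≈ 4 subjects.

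All these rates are for the effectiveness test alone; study success also requires the safety endpoint to be met.

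**The case against.** The clause carries a condition: the investigator must judge that leaving is for the subject's good. A reader might infer that any subject can be dropped at will, but the text does not say that. Since leaving changes no treatment, a failing access is hardly a reason within the rule, so the harmful case needs loose use of the clause, and nothing in the documents suggests how often it would be invoked.

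The investigator would also have to act before the event. A symptomatic target lesion leads to reintervention (Section 6.13), and an event before withdrawal remains in numerator and denominator. Certain failure of every withdrawn subject is therefore an upper bound.

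A reader might also infer that false success rises in both cohorts. For AVF the documents do not support that: nothing in the rule implies heavier withdrawal from the stent-graft arm, equal withdrawal leaves the rate at 2.5%, and PTA-only withdrawal lowers it.

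Safeguards exist. Termination reasons are tabulated and unresolved SAEs are followed (Section 5.4), the events committee adjudicates site-reported interventions (Section 12.10), and the tipping-point analysis covers every possible imputation.

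These points limit the size of the concern and make a further sensitivity analysis unnecessary. They do not close the gap: none of them obtains the missing patency outcome or enters the success rule.

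**Conclusion.** The gap is real and limited. Section 5.4 allows a discretionary, unblinded withdrawal without patency follow-up, and the primary denominator then drops the subject or counts the subject as patent.

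For AVG, a handful of selective withdrawals can take the false-success rate from 4.0% to somewhere between about 5% and 17%, depending on how many leave (2 to 6 assumed) and how well the withdrawals track failure (60% to 100% assumed). For AVF the conclusion is conditional: about 5.6% if 10% of likely failures leave the stent-graft arm only, and no inflation if withdrawal is equal.

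The documents give no expected frequency, so these figures show sensitivity and are not a forecast. Because the outcome can be collected without keeping the subject in study visits, the gap is worth closing.

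**What to change.** In Section 5.4, replace the general ground with wording to this effect: for reasons other than the three listed events, the investigator may stop a subject's study visits and study-specific assessments. Unless the subject withdraws consent, target-lesion and access-circuit interventions, thrombosis, abandonment, SAEs and UADEs continue to be collected from site and dialysis-provider records. These outcomes, and the follow-up time they document, enter the primary TLPP analysis under Sections 9.8 and 9.10.

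Leave the rule for transplant, explant and abandonment as it stands, so that the new text does not contradict it. No sensitivity analysis is needed beyond the planned tipping-point analysis, and the planned tabulation of termination reasons is enough to describe these stops.

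The cost is a short protocol amendment and record retrieval for a few subjects. Sites whose investigator does not oversee dialysis must already obtain information from the dialysis provider for the clinic visits (Sections 6.5, 6.7, 6.9 and 6.11).
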